For this open access phase 1 dose finding study, GW Pharmaceuticals and the Food and Drug Administration (FDA) have approved, based on the data from the studies mentioned above, to begin CBD with a starting dose of 5mg/kg/day in twice daily dosing. The titration of CBD is to be an initial dose of 5 mg/kg/day given in two divided doses and titrated by 5 mg/kg/2 weeks up to 25 mg/kg/day; additional increases in dosing, by 5mg/kg/day up to a maximum of 50 mg/kg/day may be instituted at the discretion of the treating PIs Patients will be monitored for adverse events and the dose reduced or the titration slowed if there are intolerable side-effects. The dose may be maintained at any point in the titration if seizures are completely controlled or there are dose-limiting side effects. This titration is overall slower than the titration in other Expanded Access Programs approved by GW Pharmaceuticals and the FDA. The titration in those programs (N=151 patients enrolled thus far) is typically initiated at the dose of 2-5 mg/kg/day followed by increases of 5 mg/kg/week up to 25 mg/kg/week; several investigators reported anecdotal use of the CBD oil (Epidiolex) in doses up to 50mg/kg/day. With this titration schedule, CBD is tolerated well with only 2/151 (1.3%) patients discontinuing CBD because of adverse events. It is expected that an even slower titration schedule proposed in our study will result in less adverse events and that this slower titration schedule will be better or equally well tolerated.

CBD Supply and Dispensing:

GW Pharma will provide its investigational cannabidiol (CBD) product, Epidiolex®, free of charge for this study. GW will export Epidiolex® in finished form to:

Catalent CTS (Clinical Trial Supplies), LLC.,
[name]
[name]
[name]

[name] will order Epidiolex from Catalent CTS using DEA Form 222 in amounts and at times that are sufficient to provide ongoing treatment to patients in accordance with the study protocol.

GW Pharma is contracted to provide CBD for up to 70 patients, at the maximum dose allowed, throughout their participation in this study.

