- Development of anemia with Hemoglobin <10 or Hematocrit <30 or WBC < 2000

If the subject wishes to discontinue the study drug for any reason, the subject will be seen for an early termination visit/end of study visit. The early discontinuation visit will include a CBC, CMP, UA and an ECG.

Study Design

Dosing Adjustment/Schedule:

The titration of CBD will start with a dose of 5 mg/kg/day given in two divided doses and titrated by 5 mg/kg/2 weeks up to 25 mg/kg/day; in some patients additional titration by 5mg/kg/day every 2 weeks upto 50mg/kg/day may be instituted at the discretion of the PI upon discussion with the Co-PI ([name]) Patients will be monitored for adverse events and the dose will be reduced or the titration slowed if there are dose-limiting side-effects.

For any clinically significant ($> 3 \times \text{ULN}$) elevation of ALT or AST, the following laboratory measures, at minimum, should be assessed within 72 hours: repeat ALT/AST, total bilirubin, alkaline phosphatase, and GGT.

- Epidiolex® will be discontinued in patients who have:
 - ALT or AST $>8 \times \text{ULN}$
 - ALT or AST $>5 \times \text{ULN}$ for more than 2 weeks
 - ALT or AST $>3 \times \text{ULN}$ **and** (TBL $>2 \times \text{ULN}$ **or** INR >1.5)
 - ALT or AST $>3 \times \text{ULN}$ with the appearance of fatigue, nausea, vomiting, right upper quadrant pain or tenderness, fever, rash, and/or eosinophilia ($>5\%$)

All trial subjects with elevated LFTs will be followed until all abnormalities return to the baseline state as assessed by the investigator with AST/ALT $< 3 \times \text{ULN}$.

If a subject has elevated LFTs ($>3 \times \text{ULN}$) and is on valproic acid the subject must stop the CBD and the LFTs must be monitored until the return to baseline state. If the subject has shown an improvement in their seizure frequency with the addition of CBD the option to “rechallenge” CBD will be at the discretion of the study PI. It would require that the subject taper off valproic acid and be on a stable dose of antiepileptic medication for 30 days prior to restarting the CBD. They would have repeat baseline labs (CBC, CMP and AED levels) prior to restarting the CBD.

The dose may be maintained at any point in the titration if seizures are controlled (no seizures since last medication adjustment) or there are limiting side effects, or the maximum dose is reached.

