While the dose of 25 mg/kg/day divided into two daily doses will be the standard maximum dose, patients who did not achieve complete seizure control but have exhibited clear improvements in seizure control (e.g., minimum decrease in seizure frequency by 50%) and who have no or minimal side effects of the CBD oil additional increases by 5 mg/kg/day every 2 weeks up to the maximum dose of 50 mg/kg/day may be instituted if both PIs ([name] & [name]) agree that this is in the best interest of the patient. This approach mimics clinical practice as antiepileptic drugs are typically adjusted based on clinical response and presence or absence of side effects.

If a subject experiences a “clinically significant” or “dose limiting” AE or SAE attributable to CBD, the investigator will determine if a dose reduction or taper is necessary. Dose decreases will occur if the patient needs to be tapered off CBD (dose-limiting side effects or lack of tolerability); these decreases will occur in 5 mg/kg/day increments every two week (or at a rate that is felt appropriate by the treating provider).

The CBD cannot be stopped all at once as this could cause the patients seizures/epilepsy to become worse.

The participant may be maintained on a dose lower than maximum amount (50mg/kg/day) if that dose, in the opinion of the patient, LAR, and the study physician, has adequately improved their seizure frequency or severity. The investigator, in consultation with the subject and/or caregiver, will determine when an adequate level of seizure frequency and/or severity of control has been achieved.

Once the subjects reach the dose of 10 mg/kg/day further dose adjustments (upward or downward) can be made biweekly at study visits in order to evaluate safety and establish a target dose up to a maximum dose of 50mg/kg/day in twice daily dosing. Dose adjustments (upward, downward, or taper) may continue until seizure control reached (target dose), maximum dose reached, or dose-limiting side effects are experienced.

Patients referred to the CBD study and approved by the CBD Treatment Approval Committee may have an enrollment visit combined with Study Visit 1 (Day 0), at the discretion of the investigator.

Enrollment Visit Procedures:

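### The protocol contradicts itself on which children may go above 25 mg/kg/day and on whose approval that needs

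*Protocol*

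**What the plan says.** Five places in the protocol govern doses above 25 mg/kg/day. They are labelled A to E here.

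- **A. Titration paragraph under Previous Human Experience with CBD.** Increases "up to a maximum of 50 mg/kg/day may be instituted at the discretion of the treating PIs". The next sentence has the dose reduced or the titration slowed for intolerable side effects.
- **B. Opening paragraph of Dosing Adjustment/Schedule.** In some patients, further titration to 50 "may be instituted at the discretion of the PI upon discussion with the Co-PI". The next sentence has the dose reduced or the titration slowed for dose-limiting side effects.
- **C. Same section, the paragraph on exceeding the usual ceiling.** It begins "While the dose of 25 mg/kg/day divided into two daily doses will be the standard maximum dose". It then describes an exception for "patients who did not achieve complete seizure control but have exhibited clear improvements in seizure control (e.g., minimum decrease in seizure frequency by 50" per cent) and "who have no or minimal side effects of the CBD oil", provided that both PIs agree it is in the patient's best interest.
- **D. Same section, a few paragraphs after C.** "Once the subjects reach the dose of 10 mg/kg/day further dose adjustments (upward or downward) can be made biweekly at study visits", to find a target dose of at most 50 mg/kg/day. Adjustment ends at seizure control, the maximum dose or dose-limiting side effects.
- **E. Procedures for Study Visits 5 and 6.** The dose goes above 25, and not above 50, in some cases where both PIs agree.

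The week-by-week schedule in Dosing Adjustment/Schedule stops at 25 and contains no rule above it. The SAP repeats the figures 25 and 50 without a condition or a decision-maker.

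**The concern.** These rules decide when a child may be taken to as much as double the standard maximum dose. The protocol's own support is thinner there: it describes earlier titration as typically reaching 25 mg/kg/day and calls use up to 50 anecdotal. A safeguard on the highest exposures should not depend on which paragraph a clinician happens to follow.

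There is also a consequence for reporting. Specific Aims, item 2a, lists change in seizure frequency at doses between 5 and 50 mg/kg/day as an outcome. If C was followed, the group above 25 consists of children who had already improved and tolerated the drug well. If D was followed, it can include children with little response. The two groups would be read differently.

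**Working it through.** The plan gives no figure to reproduce, so the check is a comparison of texts. The only arithmetic is the ratio of the two ceilings, 50/25 = 2.

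**Step 1. The rules side by side, for going above 25 mg/kg/day.**

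| Text | Approval | Response condition | Tolerability condition |
|---|---|---|---|
| A | Discretion of the treating PIs | None stated | Reduce or slow if intolerable |
| B | PI's discretion after discussion with the Co-PI | None stated | Reduce or slow if dose-limiting |
| C | Both PIs agree | Clear improvement without full control; 50% given as an example | No or minimal side effects |
| D | None named | None to enter; stop at seizure control | Stop at dose-limiting side effects |
| E | Both PIs agree | None stated | None stated |

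All five give 50 as the upper limit. They differ on approval and on eligibility.

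**Step 2. The rules applied to three children at 25 mg/kg/day.** The children are hypothetical, and their response figures are chosen only to separate the rules.

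1. *Seizures down 60%, no side effects, PI in favour, Co-PI opposed after discussion.* B permits the increase, because discussion has taken place and the discretion is the PI's. C and E do not, because both PIs have not agreed. A is unclear. D names no approval step.
2. *Seizures down 20%, no side effects, both PIs in favour.* The child falls outside the example in C. A, B and E do not exclude the child. D allows upward adjustment to continue, since none of its stopping conditions is met.
3. *Seizures down 60%, side effects more than minimal but not dose-limiting, both PIs in favour.* The child falls outside the tolerability condition in C. B and E do not exclude the child, nor does A unless the effects are judged intolerable. D allows adjustment to continue.

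**Step 3. How firm each conflict is.** Child 1 is a direct conflict between B and both C and E. Children 2 and 3 show a conflict between C and D, two paragraphs of one section. It does not rest on silence, because D states that upward adjustment may continue to 50 and lists what ends it. The difference between C and each of A, B and E on response is weaker, because A, B and E say nothing about response. No text says which rule prevails.

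**The case against.** The best defence is that most of this is summary against detail. B opens the section with a general statement about some patients, and C then says which patients. A and E are silent on patient criteria rather than contrary to C. D can be read as setting the timing of adjustments, with the conditions in C taken as already stated.

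Much of that stands for A, B and E on eligibility. It does not reconcile B with C on approval, since consulting a colleague is not the same as needing that colleague's agreement. Nor does it settle D, which starts at 10, runs to 50 and does not refer back to C.

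Several stronger readings are tempting, and the documents do not support them:

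- *D is unconditional.* It has stopping conditions. What it lacks is the entry conditions in C.
- *A and B have no tolerability rule.* Each has one, though weaker than that in C.
- *C forbids escalation below a 50% response.* The figure is an example, and the limit is implied by a standard maximum with a described exception, not written as a prohibition.
- *E conflicts with C.* The two agree on approval.
- *Results above 25 mg/kg/day cannot be interpreted.* The SAP tabulates safety overall and its longitudinal model has no dose term, so no planned analysis depends on the above-25 group. Under any of these rules, children reach those doses through clinical judgement after treatment starts. A single rule would make that selection known but would not remove it.

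**Conclusion.** The contradiction is real on two points: approval (B against C and E) and eligibility (C against D). In each, the same child could be held at 25 mg/kg/day under one paragraph and taken towards 50 under another, so the ceilings differ by up to a factor of two. How many children this touched cannot be worked out. The SAP reports 89 enrolled and does not say how many went above 25.

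The approval conflict assumes that the two PIs in C and E are the PI and Co-PI in B. Names are removed from the public text, so this cannot be checked. The eligibility conflict assumes that D means what it says up to 50 mg/kg/day and is not tacitly limited by C.

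No planned numerical result changes. The point should be corrected because it concerns a stated dose safeguard in children and because it leaves the make-up of the above-25 group undefined for the Specific Aims outcome. No view is taken here on which rule is right.

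**What to change.** Reconcile the titration paragraph under Previous Human Experience, the opening of Dosing Adjustment/Schedule, and the two conflicting paragraphs later in that section. They should state one eligibility condition and one approval rule for doses above 25 mg/kg/day. The procedures for Study Visits 5 and 6 should cross-refer to that statement. The choice of rule is the sponsor's. The cost is protocol wording.

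The SAP describes enrolment and the one-year analysis in the past tense, so new wording will not change what was done in those children. For patients already treated above 25 mg/kg/day, report how many there were, and which condition and which approval applied, wherever results at those doses are described. This costs a review of dosing and approval records for those patients, and no new data collection if those records exist.

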The specific goals of this phase I dose-finding study conducted in consecutively enrolled patients 1-18 years of age are to prospectively and longitudinally assess the safety and tolerability, including cognitive effects, of CBD at various doses between 5mg/kg/day and 25mg/kg/day with additional titration in some subjects up to 50mg/kg/day. In order to participate in the study, participants will need to fulfill the inclusion and exclusion criteria.

The goal of the study is to fulfill the mandate of “Carly’s Law” and to provide patients with debilitating epileptic conditions with access to CBD as an add-on treatment. Other care including routine neurological care that is not related to participation in the CBD study will need to be provided by patients’ primary/current treating neurologist.

Specific Aims:

The goals of this phase 1 dose-finding study are to assess the safety and tolerability, including cognitive effects, of CBD in patients with epilepsy who have failed several standard treatments as indicated in the inclusion criteria:

1. The safety outcome measures will include:
 - a. Severe adverse events (increase in seizure frequency by more than 100% leading to emergency room visit or hospitalization),
 - b. Change in resting blood pressure or heart rate by 25% if considered significant by managing neurologist,
 - c. Any change in laboratory tests considered by managing neurologists as clinically significant.
2. The seizure frequency and severity outcome measures will include:
 - a. Change in seizure frequency as measured in total number of seizures per month at various doses of CBD between 5 and 50 mg/kg/day,
 - b. Change in seizure severity as measured by the Chalfont Seizure Severity Scale (Duncan & Sander, 1991, JNNP).
3. Other data that will be collected on all enrolled participants include:
 - a. videoEEG (30 minute to 60 minutes to include wake and sleep if possible,
 - b. Cognitive and Developmental Assessment (NIH Toolbox and NIH Common Data elements, ABAS-II, and Bayley Scales),
 - c. Quality of Life Childhood Epilepsy,
 - d. Adverse Event Profile,
 - e. Emotional Measure from the NIH Toolbox and Bayley Scales
 - f. Social Determinants of Health (SDH).
 - g. Columbia Suicide Severity Rating Scale (C-SSRS)
 - h. Child Behavioral Checklist Assessment

Previous Human Experience with CBD use in Epilepsy patients:

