^aAn EEG will be performed at the first of the follow up study visit where the Principal Investigator determines the patient has reached their target dose of CBD. At the discretion of the investigator, an additional EEG may be performed at follow up visits, depending on clinical course.

^bNIH Toolbox Measures include: For ages 3-6 years: Dimensional Change Card Sort Test (DCCS), Flanker Inhibitory Control and Attention Test, Picture Sequence Memory Test, Picture Vocabulary, Oral Reading Recognition test (for children who have developed letter and/or word recognition skills). For ages 7-14 years: Dimensional Change Card Sort Test (DCCS), Flanker Inhibitory Control and Attention Test, Picture Sequence Memory Test, Picture Vocabulary Test, Oral Reading Recognition Test, List Sorting Working Memory Test, Pattern Comparison Processing Speed Test. For ages 15-18 years: Dimensional Change Card Sort Test (DCCS), Flanker Inhibitory Control and Attention Test, Picture Sequence Memory Test, List Sorting Working Memory Test, Pattern Comparison Processing Speed Test, Reading Recognition Test. For participants between the ages of 1 year (12 months) and less than 3 years of age, and/or who are unable, due to cognitive impairment, to complete the Cognitive subtests from the NIH Toolbox, their legal guardian will be asked to complete the Adaptive Behavior Assessment Scale – II (ABAS-II). The ABAS-II measures adaptive behavior, using parent-report to evaluate function across a variety of environments. Test results include four domain composite scores (Conceptual, Social, Practical, and General Adaptive Composite) and 10 skill area scores (Communication, Community Use, Functional Academics, Health and Safety, Home or School Living, Leisure, Self-Care, Self-Direction, Social, and Work/Motor). For participants < 3 years of age, Bayley Scales of Infant and Toddler Development®, Third Edition (Bayley-III®)-Functional Assessments will be completed by the parent or LAR of the participant, instead of the NIH Cognitive assessments.

^cDuring any early termination or unscheduled visit, individual decision will be made by the managing study doctor regarding further participation, medication titration (up or down), medication wean, etc. If the patient and provider agree on terminating participation prior to 1 year visit, the following data points will be collected at that visit (or at year 1 visit).

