- NIH Toolbox Dimensional Change Card Sort Test (DCCS) – cognitive flexibility
- NIH Toolbox Flanker Inhibitory Control and Attention Test – attention and inhibitory control
- NIH Toolbox Picture Sequence Memory Test – episodic memory
- NIH Toolbox Picture Vocabulary Test – vocabulary knowledge
- NIH Toolbox Oral Reading Recognition Test - reading
- NIH Toolbox List Sorting Working Memory Test – working memory
- NIH Toolbox Pattern Comparison Processing Speed Test – speed of processing

For participants who are unable, due to cognitive impairment, to complete the Cognitive subtests from the NIH Toolbox, their legal guardian will be asked to complete the Adaptive Behavior Assessment Scale – II (ABAS-II). The ABAS-II measures adaptive behavior, using parent-report to evaluate function across a variety of environments. Test results include four domain composite scores (Conceptual, Social, Practical, and General Adaptive Composite) and 10 skill area scores (Communication, Community Use, Functional Academics, Health and Safety, Home or School Living, Leisure, Self-Care, Self-Direction, Social, and Work/Motor).

For participants < 3 years of age, Bayley Scales of Infant and Toddler Development®, Third Edition (Bayley-III®)-Functional Assessments will be completed by the parent or LAR of the participant, instead of the NIH Toolbox Cognitive assessments.

- Quality of Life in Childhood Epilepsy Questionnaire– QOLCE is composed of 16 subscales assessing seven domains of HRQL (physical function, social function, emotional well-being, cognition, behavior, general health and general quality of life)
- Adverse events profile (AEP) – Pediatric equivalent is a systematic screening instrument with a brief 19-item self-report format. The AEP is used to assess adverse effects of AEDs and improve subjective health status.
- NIH Toolbox for Emotional Assessment: Emotion Measures from the NIH Toolbox will be administered to each participant and/or their legal guardian. The Emotion Measures from the NIH Toolbox assess four major domains: Negative Affect (NA), Psychological Well-Being (PWB), Social Relationships (SR), and Stress/Self-Efficacy (SSE).

For participants ages 3 – 7, the following age-appropriate subtests from the NIH Toolbox Emotion Parent Proxy Battery will be administered:

- Negative Affect
 - o NIH TB NA Anger – Parent Report
 - o NIH TB NA Fear-Over Anxious Parent Report for Children
 - o NIH TB NA Fear-Separation Anxiety Parent Report FFSF

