- NIH Toolbox Picture Sequence Memory Test – episodic memory
- NIH Toolbox Picture Vocabulary Test – vocabulary knowledge
- NIH Toolbox Oral Reading Recognition Test - reading
- NIH Toolbox List Sorting Working Memory Test – working memory
- NIH Toolbox Pattern Comparison Processing Speed Test – speed of processing

For participants who are unable, due to cognitive impairment, to complete the Cognitive subtests from the NIH Toolbox, their legal guardian will be asked to complete the Adaptive Behavior Assessment Scale – II (ABAS-II). The ABAS-II measures adaptive behavior, using parent-report to evaluate function across a variety of environments. Test results include four domain composite scores (Conceptual, Social, Practical, and General Adaptive Composite) and 10 skill area scores (Communication, Community Use, Functional Academics, Health and Safety, Home or School Living, Leisure, Self-Care, Self-Direction, Social, and Work/Motor).

- For participants < 3 years of age, Bayley Scales of Infant and Toddler Development®, Third Edition (Bayley-III®)-Functional Assessments will be completed by the parent or LAR of the participant, instead of the NIH Toolbox Cognitive assessments.
- Social Determinants of Health (SDH) – selected SDH variables will be re-assessed at year 1 and annually thereafter:
 - Biosocial variables (age, date of birth)
 - Socio-demographic variables (education, family structure, family income, financial strain, health insurance status, overall health, health care access/utilization)
 - Psychosocial variables (health literacy, health information sources, social stress, social support, optimism, self-efficacy)
 - Behavioral variables (physical/social activity)
 - Individual-level social relationship domains (exposure to discrimination/violence, self esteem rating, religious participation)
 - Geocodable information (address to identify US census tract/block) to link to neighborhood/community-level published national/state socioeconomic and racial/ethnic composition indicators
 - Study Drug CBD Medication Order and/or adjustments in CBD dosing (as described under Dosing Adjustment/Schedule section above)

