graphic techniques and summary statistics. Repeated measures linear regression models will be used to examine the changes over time using random effects for participant. Various measure of control will be defined (i.e. 10% reduction in seizure frequency, 25%, 50%, etc.) will be used to assess the duration, pattern and durability of control. Measuring the percent of time over the duration of follow up that control is obtained will summarize effectiveness. The variability of control will be assessed once control is achieved to assess the reliability and stability of the control. Subgroups will be examined (i.e. are males different than females in response, younger versus older, etc.)

As an observational study, power is not a relevant parameter. However, when the sample size is 100, a two-sided 90.0% confidence interval for the estimated mean will extend 0.164 standard deviation units from the observed mean, and the confidence interval is based on the large sample z statistic.

Other data that will be collected on all enrolled patients include:

- c. EEG (30-60 minute),
- d. Pediatric Cognitive performance (NIH Toolbox),
- e. Quality of Life in Childhood Epilepsy Questionnaire,
- f. Adverse Events Profile,
- g. NIH Emotional Assessment,
- h. Social Determinants of Health (SDH),
- i. Columbia-Suicide Severity Rating Scale (C-SSRS) Questionnaire,
- j. Child Behavioral Checklist Assessment.

The analyses of the exploratory data will include descriptive statistics, graphic techniques, and repeated measures random coefficient models using techniques as described above for the frequency and severity of seizures endpoints.

IRB:

The University of Alabama at Birmingham IRB will be utilized for this study.

Publication Strategy:

Standard scientific outlets will be utilized for this purpose. Study results will be presented in part or in its entirety at the Annual Meetings of the American Academy of Neurology, Annual Meetings of the American Epilepsy Society, and Child Neurology Society. Manuscripts resulting from this work will be submitted to high-impact scientific journals e.g., Neurology or Epilepsia.

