## Statistical Analysis Plan

The UAB Pediatric CBD Program enrolled 89 treatment resistant epileptic children ages 1-19 years old. All study participants received Epidiolex drug (Cannabidiol; CBD) as an add-on to their previously stable anticonvulsive treatment after baseline assessment. Participants received a starting dose of CBD at 5 mg/kg/day in twice daily dosing and titrated by 5 mg/kg/2 weeks up to 25 mg/kg/day, with a maximum dose of 50 mg/kg/day. Seizure frequency, severity, and adverse events together, with other clinical participant measures, were assessed at baseline and bi-weekly for the duration of the study.

The first 12-months (1-year) of follow-up data were analyzed as follows:

1. The primary outcome measures included:

- a. Severe adverse events (increase in seizure frequency by more than 100% leading to emergency room visit or hospitalization),
- b. Change in resting blood pressure or heart rate by 25% if considered significant by managing neurologist,
- c. Any change in, CBC, CMP, Liver function tests (LFTs), Urinary Analysis or Antiepileptic drug (AED) levels considered by managing neurologists as clinically significant. Clinically significant will be determined by using the Common Toxicity Criteria for Adverse Events (CTCAE) Version 4.03. Adverse events (AE) categorized as a grade 3 or above will be considered clinically significant. Adverse Events graded 4 or above will be considered severe adverse events (SAE).

The analysis plan was focused on safety. The information on safety was tabulated as the percent of participants with each safety outcome AE and SAE, or others reported as meaningful as well as the number of occurrences of each AE and SAE. This enabled an event rate calculation per exposure time as well as the average number of occurrences per participant with an AE or SAE.

2. The secondary analysis assessed the frequency and severity of seizure outcome measures to include:

- a. Mean (SD) and median (IQR) decrease in seizure frequency as measured in total number of seizures per month.
- b. Mean (SD) and median (IQR) decrease in seizure severity as measured by the Chalfont Seizure Severity Scale (Duncan & Sander, 1991, JNNP).

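### Cognitive effects are part of the stated goal, but the SAP does not analyse them, and a child who becomes unable to do the NIH Toolbox leaves its change analysis

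*Protocol*

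**What the plan says.** The protocol states the goal twice. In the Design part of the Introduction the study is to "prospectively and longitudinally assess the safety and tolerability, including cognitive effects, of CBD at various doses". Specific Aims repeats it: "The goals of this phase 1 dose-finding study are to assess the safety and tolerability, including cognitive effects, of CBD".

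In the protocol's Data Analysis section, cognition is neither a primary nor a secondary measure. It stands among the other data, to be analysed by descriptive statistics, graphs and "repeated measures random coefficient models using techniques as described above for the frequency and severity of seizures endpoints". No cognitive endpoint, score type or rule for a change of instrument is given.

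The SAP states "The analysis plan was focused on safety". It covers adverse events, vital signs, laboratory changes, seizure frequency and seizure severity over the first 12 months in 89 children. Its nearest reference to cognition is a general mention of other clinical measures, with no analysis attached.

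The instrument rule appears under Study Visit 1, again under Study Visits 10, 14 and 18, and again for early termination (in Unscheduled Study Visit):

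- Ages 3-6: five Toolbox subtests.
- Ages 7-18: the same five, plus List Sorting and Pattern Comparison.
- Unable to do the Toolbox: "For participants who are unable, due to cognitive impairment, to complete the Cognitive subtests from the NIH Toolbox, their legal guardian will be asked to" (fill in the ABAS-II).
- Under 3: Bayley-III functional scales, which "will be completed by the parent or LAR of the participant, instead of the NIH Toolbox Cognitive assessments".

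Footnote b of the Schedule of Events differs in two places. It widens the ABAS-II group: "For participants between the ages of 1 year (12 months) and less than 3 years of age, and/or who are unable, due to cognitive impairment". It also omits Picture Vocabulary at ages 15-18.

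**The concern.** Cognitive harm is one of the tolerability questions the study set out to answer in children. If the SAP is followed, the cognitive test scores are collected and not analysed. If the protocol's exploratory models are run instead, the scores they need go missing for a reason tied to the outcome: the rule takes away the Toolbox score when a child becomes too impaired to produce one. The children with the most marked decline could be the ones absent from the follow-up mean, and a finding of no cognitive effect could partly reflect their absence.

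**Working it through.** **1. Follow one child through the rule.** At Study Visit 1 the child completes the Toolbox, so no ABAS-II is taken. At month 6 the child cannot complete it because of cognitive impairment, so the guardian completes the ABAS-II. The record then holds a performance score at baseline and a guardian rating at follow-up: no subtest in common and no change score. The same can happen at early termination, which may follow an unscheduled visit for side effects. A random coefficient model keeps this child's baseline score but must infer the follow-up from children who could still be tested. That is sound only if the loss is explained by scores already observed. Here it depends on the score that was not observed.

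**2. Reproduce the plan's precision figure.** Data Analysis gives a two-sided 90% confidence interval for a mean at n = 100, adults and children combined. Half-width = z(0.95)/√n = 1.6449/10 = 0.164 SD, as stated. The documents give no figure for cognition. The same formula gives 0.174 SD for n = 89, 0.197 for n = 70 and 0.233 for n = 50.

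**3. Size of the bias, as an illustration.** Assume that change scores are normal and that the worst fraction q, among children who did the Toolbox at Study Visit 1, is lost. The mean of the rest is too favourable by φ(z_q)/(1 − q) SD. If inability correlates only 0.5 with change, the bias is half of that.

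| q lost | φ(z_q) | Bias, full dependence | Bias, correlation 0.5 |
|---|---|---|---|
| 2% | 0.0484 | 0.0484/0.98 = 0.049 SD | 0.025 SD |
| 5% | 0.1031 | 0.1031/0.95 = 0.109 SD | 0.054 SD |
| 10% | 0.1755 | 0.1755/0.90 = 0.195 SD | 0.097 SD |
| 20% | 0.2800 | 0.2800/0.80 = 0.350 SD | 0.175 SD |

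With full dependence, a 10% loss exceeds the stated half-width of 0.164 SD, and also 0.174 SD at n = 89. It is about equal to the half-width at n = 70 and below it at n = 50.

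**4. Age limits.** Compare the subtest lists on each side of each limit.

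- Age 6 to 7: all five earlier subtests continue, so change on those five can be computed.
- Age 14 to 15: nothing changes under the visit text. Under footnote b, six of seven subtests continue and Picture Vocabulary is lost.
- Under 3 to 3: under the visit text, nothing carries over from the Bayley-III to the Toolbox.

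The documents give no age distribution. If entry ages are uniform from 1 to under 19, the share crossing age 3 is 0.5/18 = 2.8% by month 6 (89 × 0.028 = 2.5 children) and 1/18 = 5.6% by month 12 (89 × 0.056 = about 5 children).

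**5. Timing.** The narrative says that cognitive testing is done at Study Visit 1 and then yearly. The visit list and the Schedule of Events place it at months 6, 24 and 48, with none at month 12. On the visit list, the SAP's 12-month window holds one scheduled follow-up test, at month 6.

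**The case against.** The best defence is that cognition was placed among the exploratory data with a stated, if general, analysis. One instrument across ages 1 to 18 is hard to find, and the protocol describes the Toolbox as usable over a wide range of ability. Cognitive worsening that is clinically evident would also be recorded as an adverse event, graded and tabulated under the SAP. The QOLCE has a cognition domain and is given at Study Visits 1, 10, 14 and 18 with no stated switch of form. This stands in part: the SAP is not blind to overt cognitive harm. But adverse event reports do not replace performance testing, and the SAP does not analyse the QOLCE either.

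Four stronger readings are tempting, and the documents do not support them.

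- A reader might infer that any decline costs a child the change score. A child who declines but still completes the Toolbox keeps it.
- A reader might infer that every age limit breaks the series. Only age 3 does so fully, and only under the visit text.
- A reader might extend the point to the emotional batteries. Guardians of children aged 8-12 still complete a proxy battery, and five of the ten parent measures for ages 3-7 continue in it. Nine of eleven measures in the 8-12 self-report battery continue at 13, and eight of twelve at 18. These batteries also measure emotion, not cognition.
- A reader might think that ABAS-II at Study Visit 1 for all children under 3 would supply a common scale. It would not for a child who can do the Toolbox after turning 3, because that child is then given no ABAS-II. The SAP is also written after enrolment, so baseline data can no longer be added.

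Finally, that the instrument is chosen afresh at each visit is inferred from the rule being repeated; the protocol does not say so outright.

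**Conclusion.** The concern holds in this form. Cognition is in the goal, the SAP text from its main heading on has no cognitive analysis, and no rule deals with a move from the Toolbox to the ABAS-II. Loss through such a move depends on the outcome and biases the Toolbox change towards no cognitive effect. The number of children affected is unknown, and no planned table would show it. The illustrative bias is about 0.11 SD at 5% loss and 0.20 SD at 10% under normality and full dependence, and half of that at a correlation of 0.5. The break at age 3 is a smaller matter: about 3% of children by month 6 and 6% by month 12 if ages are uniform, and it is not in itself tied to decline.

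**What to change.** Add cognition to the safety section of the SAP.

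1. Report change from Study Visit 1 within instrument, in age-normed scores, using only subtests given at both visits.
2. Beside those scores, tabulate the number and percentage of children who completed the Toolbox at Study Visit 1 and could not at follow-up, with the reason where recorded. Add a sensitivity analysis that counts those unable because of cognitive impairment as worsened.
3. Reconcile footnote b with the visit text on ABAS-II under age 3 and on Picture Vocabulary at 15-18. Reconcile yearly testing with the scheduled months 6, 24 and 48. State which instrument each child received at each visit.

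The cost is a few tables and one sensitivity analysis, mostly from data already collected; reasons for non-completion may have to be retrieved from source records. The downside is small: some children are untestable on the day for passing reasons, so the reason must be shown and only inability from cognitive impairment counted as worsening.
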